A maximum of 30 subjects will be included in the imaging portion of this study. Similar to the cold / dress rehearsal volunteers, these participants will complete an initial dress rehearsal visit at the WCIBMI to walk through the study procedures. However, the full study participants will also return to the WCIBMI on a second date to complete the imaging study with the ¹¹C-nicotine ecigarette. Bergstrom et al. (Clinical Pharmacology and Therapeutics, 1995; 57(3):309-17) has reported a relative percent deviation of 34% in the total dose released following 5 minutes of aerosol inhalation (15.4 +/- 5.3%). Assuming an alpha value of 0.05 and a power of 0.8, a sample size of at least 8 subjects is required to observe significant differences in the dose released. One of the aims of this study is to evaluate the next generation PET/CT technology that may exhibit different variance. As a result, larger populations are likely required in order to evaluate a significant difference between the groups. If the power is set to 0.95 to account for this, then the number of subjects required per group is 14. In order to ensure significance and to account for any subjects that do not comply, a total of 30 subjects is requested. Subjects may enroll up to two times (i.e., repeat the imaging study with ¹¹C-nicotine one additional time), but the second enrollment must be at least one week after the first visit.

[figure not shown]

Figure: Schematic of participant procedures. After determined eligible via eligibility surveys, participants will be invited to the WCIBMI to complete the relevant consent forms. If they are participating in the full study, they will first participate in the dress rehearsal, and then study personnel will schedule a time for the participant to return to the WCIBMI and complete the full, imaging portion of the study. If they are participating in only the dress rehearsal, they will not receive any radiation or imaging, and they will receive compensation at the end of the dress rehearsal.

Measurement / Instrumentation

PET/CT imaging will be predominately performed on the next generation digital photon counting PET/CT (Vereos); however, the mobile conventional PET/CT (Gemini TF 64) that is parked on the Martha Morehouse facility will serve as a backup PET/CT imaging system in case of any technical reasons. Our main focus is to utilize the digital PET system, but we need and want the

Version: December 20, 2017 Page 5 of 16

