option to perform imaging on the conventional PET/CT system in case there is a technical issue causing unavailability of the digital PET system.

Both systems are able to acquire using listmode with time-of-flight encoding.

Both systems have an internal closed circuit video system that will record every aspect during the subjects' presence in the room. Access to these video recordings will be restricted to authorized study personnel and used only for the purpose of reviewing the procedure and correlating placement and timing of the e-cigarette and ¹¹C-nicotine inhalation with the acquired PET images.

The PET acquisition will be initiated prior to the placement of the prepared e-cigarette in the field of view.

Prior to the imaging examination using the ¹¹C-nicotine prepared e-cigarette, the subject will be trained using a full dress rehearsal with no radioactivity.

For the imaging examination, the subjects will be supine on the imaging bed proximal to the PET camera while they are instructed when and how to vape. Subjects will vape normally and exhale freely into a directional airflow, ensured by a fan and a plastic bubble placed on the backside of the PET system combined with a suction vacuum pulling the air through a HEPA filter. Once vaping is completed, the e-cigarette will be taken from the subject, and the remaining residual ¹¹C-nicotine activity within the e-cigarette will be determined using a well counter. The delivered dose will then be determined as the total activity in the e-cigarette liquid prior to vaping minus the decay corrected activity in the e-cigarette liquid after vaping.

Immediately and during the vaping, the dynamic and continuous PET imaging will be performed using multiple bed positions to image from the vertex of the skull to the abdomen.

A very low dose CT attenuation scan (0.8 mSv) will be acquired for attenuation correction and anatomic correlation prior to and after the emission scanning.

Schematic of the PET/CT for e-cigarette vape/aerosol trapping

The diagrams below show the experimental setup. As has been reviewed with the OSU Radiation Safety Officer (RSO), we will trap the exhaled ¹¹C-nicotine e-cigarette vape only via positive airflow through the PET gantry and subsequent suction through a HEPA filter vacuum system.

[figure not shown]

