All PET/CT imaging will be performed using the Vereos digital PET/CT and/or the mobile conventional Gemini PET/CT systems located at the WCIBMI. The subject will lay supine and therefore must be able to inhale/vape in this position. The subject will be placed in the PET camera as to generate axial slices in the following regions: head/neck (e.g., brain, oral cavity, and throat) and thorax (e.g., trachea, lungs). CT image acquisition will be at the lowest dosages possible for accurate anatomic localization of ¹¹C radioactivity on the PET images (80KV, 30mAs, 3D dose modulated). Dynamic PET images will be acquired over a time period of up to 60 minutes following the start of ¹¹C-nicotine inhalation/vaping. The total PET imaging scan time will not exceed 60 minutes per subject. The total time in the imaging suite will be a maximum of 85 minutes for each subject (15 minutes prior to scanning, <5 minutes for inhalation, <2 minutes to remove ecigarette, and up to 60 minutes scanning). Once the subject leaves the imaging suite, the imaging suite will be surveyed. If the radioactivity is above background levels, the suite will be locked and the PET/CT imaging area will be considered radioactive until 20 half-lives (i.e., 406 min) have passed. The imaging area will be marked as "Do not access" until the next morning and subsequently surveyed no sooner than every 30 minutes until background levels of radioactivity are achieved.

Optimal PET imaging parameters will be utilized for each PET/CT system and, as a result, may differ between the conventional Gemini and next generation digital Vereos systems. However,

Version: December 20, 2017 Page **11** of **16**

time of flight acquisition with lost mode recording will be used on both systems. For example, the digital Vereos system is able to acquire PET images with faster timing resolution and with lower voxel sizes compared to the conventional Gemini system. The PET image acquisition parameters, however, will be held constant on each individual system.

¹¹C Labeling

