¹¹C-labeled S-nicotine will be produced at the Kinnear Road facility following a gas-phase method developed by the WCIBMI team (Gosh A. et al, Applied Radiation & Isotopes, 2017, submitted) according to applicable production guidelines for inhalants. In short, purified ¹¹C-labeled S-nicotine will be diluted with the e liquid. The ¹¹C-labeled S-nicotine concentration, radiochemical purity, and specific activity will be determined. Appropriate amount of the e liquid containing ¹¹C-labeled nicotine will be loaded in the e-cigarette cartridge. The radioactivity in the cartridge will be determined, and the e-cigarette will be placed in a lead syringe holder, which will be delivered to the WCIBMI imaging facility at Kenny Road.

¹¹C Dose

The total radioactivity in the cartridge of the e-cigarette will not exceed 9 mCi delivered to the patient. Initially, we will use a dosage of 3 mCi (Dose level A); however, if this dosage does not produce adequate image quality, the dosage will be raised to 9 mCi (Dose level B) for subsequent participants. The release of radioactivity is expected to be 15 +/- 5% during the inhalation phase (Bergstrom et al, Clinical Pharmacology and Therapeutics, 1995; 57(3):309-17). The total delivered dose to the subject will be determined and recorded.

Data Analysis

All PET images will be reconstructed to generate quantitative images for absolute determination of radioactivity distribution. Corrections for the decay of ¹¹C will be applied. The deposition will be shown in 3D and co-localized relative to the anatomy (as provided by the CT images). The total radioactivity will be determined in the head/neck and thorax (e.g., brain, oral cavity, trachea, esophagus, bronchi, lungs, and other relevant soft tissues like muscle). Analysis of other tissues within the imaging field of view may be performed if ¹¹C activity is observed.

The biodistribution, uptake, and clearance will be evaluated in the specified tissues. The results obtained using conventional PET/CT will be compared to the results obtained using the new digital technology. The percent variance in the total radioactivity will be determined at each time point for each tissue.

We are not performing intra-individual comparator examinations. We are focusing on assessing the new generation digital technology and have comparable historical benchmark data available for comparison.

Compensation

Each subject who participates will be eligible for compensation.

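### The protocol claims 0.95 power with 14 per group, but it names neither the groups nor the difference, and the second scanner group is only a backup

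*Protocol*

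**What the plan says.** **Sample size** (Protocol, Participant Procedures, Imaging Volunteers). The protocol takes the released dose from a cited study (15.4 ± 5.3%, a relative deviation of 34%). It gives at least 8 subjects at alpha 0.05 and power 0.8. It then says that the new PET/CT technology may have a different variance, and continues: "If the power is set to 0.95 to account for this, then the number of subjects required per group is 14". The total follows: "In order to ensure significance and to account for any subjects that do not comply, a total of 30 subjects is requested".

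**Scanners.** Measurement / Instrumentation puts imaging mainly on the digital system. The conventional one "will serve as a backup PET/CT imaging system in case of any technical reasons", kept as an "option to perform imaging on the conventional PET/CT system in case there is a technical issue causing unavailability of the digital PET system". The Imaging section is looser: "All PET/CT imaging will be performed using the Vereos digital PET/CT and/or the mobile conventional Gemini PET/CT systems". No section gives an allocation ratio or a minimum number per scanner.

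**Comparisons.** Data Analysis states: "The results obtained using conventional PET/CT will be compared to the results obtained using the new digital technology". It also states: "We are not performing intra-individual comparator examinations". It adds that historical benchmark data are available. Methods Overview calls the two dose levels groups, but level B is an alternate, used only if image quality at level A is inadequate. No test of A against B is planned.

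**The concern.** A power statement means something only when the comparison, the difference, the SD, the sidedness and the group sizes are known. Here the difference, the sidedness and the identity of the groups are absent. The one comparison the protocol does plan among its own subjects has a second group whose size depends on equipment downtime. That group could be small or empty, and without within-subject examinations pairing cannot make up for it.

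The reason given for moving from 0.8 to 0.95 does not connect either. Released dose, the only quantity with a stated SD, is assayed from the activity left in the e-cigarette (Measurement / Instrumentation; Imaging Visit), so scanner variance does not enter it. If the calculation is meant for PET-measured activity, no SD is given for that.

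At stake is the stated reason for exposing up to 30 people to radiation. A null conventional-versus-digital result could also be read as agreement between scanners when it reflects only a handful of conventional scans.

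**Working it through.** **Inputs from the protocol:** alpha 0.05; power 0.8 with 8 and power 0.95 with 14 per group; total 30 (2 × 14 = 28, plus 2); released dose mean 15.4, SD 5.3. **Not given:** difference, sidedness, groups, allocation. The differences and scanner splits below are therefore assumptions.

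**Step 1. Can 8 and 14 be reproduced?** Not from stated inputs, so solve backwards for the difference d (in SD units) that returns both after rounding up. The normal formulas are n per group = 2(z_alpha + z_power)²/d² for two samples and n = (z_alpha + z_power)²/d² for one sample. For two samples, two-sided, the numerators are 2(1.960 + 0.842)² = 15.70 and 2(1.960 + 1.645)² = 25.99.

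| Design | d returning both 8 and 14 |
|---|---|
| Two-sample, two-sided | 1.401–1.413 |
| Two-sample, one-sided | 1.244–1.290 |
| One-sample, two-sided | 0.991–0.999 |
| One-sample, one-sided | 0.880–0.912 |

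The figure of 14 is attainable, so it cannot be called an arithmetic error. Four different designs fit, and the protocol does not say which was meant.

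**Step 2. Does any grouping deliver 14 per group?**
- *Scanner:* planned as a comparison, but the second group is a backup with no set size.
- *Dose level:* B is conditional and sequential, may be empty, and has no planned test.
- *Historical benchmark:* one enrolled group, which a per-group 14 and a total of 30 do not describe. The sample-size text makes no link to it.

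**Step 3. Power when the backup group is small.** Pooled two-sided t-test, noncentrality d·√(n1·n2/(n1 + n2)), df = n1 + n2 − 2. Example at d = 1.41 and 25/5: 1.41 × √(125/30) = 2.88 on 28 df, critical t 2.048, power 0.79.

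| Digital/conventional | Power, d = 1.41 | Power, d = 1.0 | d detectable at 0.95 |
|---|---|---|---|
| 14/14 | 0.95 | 0.72 | 1.42 |
| 20/10 | 0.94 | 0.70 | 1.45 |
| 22/8 | 0.91 | 0.65 | 1.54 |
| 25/5 | 0.79 | 0.50 | 1.83 |
| 28/2 | 0.46 | 0.26 | 2.73 |
| 30/0 | no test | no test | – |

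The d = 1.0 column corresponds to the quoted 34% deviation, since 5.3/15.4 = 0.34. On that reading even full 14/14 groups fall well short of 0.95.

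**Step 4. What does raising the power buy against a larger SD?** Replace d by 1.41/k, with the SD k times larger in both groups.

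| k | 8/8 | 14/14 | 25/5 |
|---|---|---|---|
| 1.28 | 0.54 | 0.80 | 0.58 |
| 1.5 | 0.42 | 0.67 | 0.46 |

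The margin is real but limited, and it exists only if both groups are filled.

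**Step 5. Precision of a single group.** The 95% CI half-width is t(0.975, n − 1)·SD/√n. For n = 30: 2.045/√30 = 0.373 SD. For n = 28: 2.052/√28 = 0.388 SD. With SD 5.3 these are 1.98 and 2.06 percentage points; with an SD 1.5 times larger (7.95), 2.97 and 3.08.

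**The case against.** - **The historical benchmark may be the intended comparator.** Data Analysis mentions it directly after excluding within-subject comparison, and on that reading no internal group is emptied. The quoted 34% is about 1 SD, and a one-sample formula with rounded z values gives (1.96 + 0.84)² = 7.84, so 8, and (1.96 + 1.65)² = 13.03, so 14. This is a plausible origin of the figures. It remains an inference, it is not a per-group formula, and it does not lead to a total of 30. It shows that the intended comparison is unclear; it does not rescue the claim.
- **The power table rests on assumed differences and splits, and on equal SDs.** This is correct. The protocol's worry is a variance that differs between scanners. Simulating 25/5 at 1.41 SD with the SD 1.5 times larger on the digital system only gives power of about 0.49 pooled or 0.63 with Welch's test. If the larger SD is on the conventional system only, the pooled test's type I error is about 0.13. The exact figures should not be leaned on; the loss with severe imbalance stands.
- **The study is exploratory, no formal test is written, and 30 is a maximum.** This limits the harm and favours dropping the power claim. Nor is it detail left to an SAP, because the protocol itself states the power and uses it to justify 30.
- **Precision of the released fraction is not what the aims are about.** This is fair. It is used below only because it is the one quantity with a stated SD.

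**Conclusion.** The point holds. The protocol states a power that its own design does not secure under any of the groupings it mentions. Assuming a two-sided test and a 1.41 SD difference, moderate imbalance is tolerable (0.91 at 22/8). Serious loss begins at about 5 or fewer subjects on the backup scanner (0.79 at 25/5, 0.46 at 28/2). At an assumed 1 SD difference, power is 0.72 even with 14 in each group. The value of 14 itself is not shown to be wrong; it is unsupported. The consequence is confined to the sample-size justification and to how the conventional-versus-digital contrast is read. It should be fixed but does not threaten the study's aims.

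**What to change.** Delete the per-group 0.95 power sentence and the phrase about ensuring significance. State that scanner contrasts, and any dose-level contrasts, are descriptive and will be reported with the number per group, estimates and 95% confidence intervals. Justify the maximum of 30 by precision, for example:

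*With 30 distinct subjects a mean is estimated to within ±0.37 SD (95% CI; ±0.39 SD with 28). For the fraction released, if the SD is 5.3, this is about ±2.0 percentage points (±2.1 with 28), and about ±3.0 if the SD is 1.5 times larger.*

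Subjects must be distinct because the protocol allows a second enrolment. A regional uptake measure would suit the aims better and can replace the fraction released if its SD is stated. The sponsor should also say why the resulting precision is adequate.

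Alternatively, keep a power statement but name the comparison (for instance with the historical benchmark), its endpoint, difference, SD, sidedness and planned numbers, and restate the power it actually has.

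The cost is protocol wording only: no extra subjects and no change to procedures or to the dose-step rule. The sponsor gives up, or has to specify, a power claim.

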For those subjects that have indicated their interest to participate in the imaging study, the following additional steps will occur during the dress rehearsal visit:

- Participants will be informed about the further study details, the consent form will be reviewed and signed, and an imaging date will be scheduled.
- Participants will be given the e-cigarette that will be used in the study so that they can get accommodated to the device and practice vaping in the supine position.
- For female subjects participating in the imaging procedure, urine will collected during the screening visit to confirm that they are not pregnant.

All subjects participating in the imaging study will be required to have a full dress rehearsal at the WCIBMI prior to their imaging procedures in order to practice and be familiar with the study facilities/procedure: the gowning into hospital scrubs and protective gear, the proper posture for PET scanning, and the e- cigarette vaping and exhaling procedure. There will be no PET/CT imaging or ¹¹C-nicotine radiation exposure during the dress rehearsal.

Subjects who initially agree only to the dress rehearsal are eligible to add the subsequent imaging study without an additional dress rehearsal unless requested by the PI. The subject will complete appropriate consent documentation of their expanded participation. The dress rehearsal and subsequent ¹¹C-nicotine PET/CT imaging examination will follow the same steps.

Subject Gowning

The subject will wear hospital scrubs and personal protective gear in order to minimize any ¹¹C radioactive deposits from the exhaled vape. The subject will also wear two sets of gloves. The gowning will be guided and monitored by research project personnel.

Figure: Subject gowning procedure. Still pictures from a training video demonstrate the subject gowning procedure with personal protective gear.

Version: December 20, 2017 Page 8 of 16

Subject Positioning on the PET/CT System

After gowning, the subject will be placed on the PET/CT system. A knee support pad and a head-holder will be available and used to improve subject comfort and minimize subject motion.

Once the subject is comfortably positioned, the surview scan will be performed using CT only, and the PET/CT imaging field will be planned. Once the imaging field is determined, an attenuation CT scan of the imaging field will be acquired.

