The volunteers who participate in the dress rehearsal only (i.e., no ¹¹C-nicotine exposure and no PET/CT imaging) will receive a \$100 Visa gift card.

Subjects who participate in the complete study (i.e., dress rehearsal and ¹¹C-nicotine PET/CT imaging) will receive a \$250 Visa gift card, which will be provided to them after completion of all study requirements.

Version: December 20, 2017 Page **12** of **16**

By law, payments to subjects are considered taxable income.

Incidental Findings

Imaging incidental findings will not be observable in this study as the PET and CT imaging will not be of diagnostic quality.

RISKS, BENEFITS, SAFETY, AND CONFIDENTIALITY

Risks

Overall, the risk/benefit ratio of this study is minimal since the probability and magnitude of harm or discomfort anticipated in the study are not greater than what is ordinarily encountered during the performance of a routine PET/CT.

Minimal risk exists during any PET imaging. Risks are mainly due to potential impingement by the moving table and falling off the imaging table.

Radiation Risk

Dose Level A (3 mCi 11C-nicotine Dosage)

Participants will receive a e-cigarette with an total dosage of 3 mCi from the ¹¹C-nicotine, of which only a fraction will be inhaled by the participant. For the 3 mCi dosage, the PET radiotracer will yield minimal radiation exposure of 0.64 mSv.

The attenuation CT will add 0.8 mSv EDE to the overall dose exposure. For the 3 mCi ¹¹C-nicotine dosage, the combined and total EDE is 1.44 mSv. On average, a U.S. resident receives an annual radiation exposure from natural sources of about 3.6 mSv. The 1.44 mSv EDE is equivalent to 4.8 months or 146 days of natural radiation exposure. The calculated corresponding BEIR VII risk estimate may range from about one in 48,906 (0.002%) to about one in 20,469 (0.005%). This is considered minimal risk.

9 mCi ¹¹C-nicotine Dosage

If necessary, the ¹¹C-nicotine dosage may be raised to 9 mCi. Only a fraction of this dosage will be inhaled by the participant. From this dosage, participants will receive a minimal radiation exposure of 1.90 mSv.

The attenuation CT will add 0.8 mSv EDE to the overall dose exposure, so the combined and total EDE is 2.70 mSv for the 9 mCi ¹¹C-nicotine dosage. The 2.70 mSv EDE is equivalent to 9 months or 274 days of natural radiation exposure. The calculated corresponding BEIR VII risk estimate may range from about one in 11,575 (0.0086%) to about one in 4,845 (0.021%).

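### The protocol is inconsistent on how many attenuation CTs a session includes, and its total exposures of 1.44 and 2.70 mSv count 0.8 mSv of CT and one session although a second session is allowed

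*Protocol*

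**What the plan says.** Four places in the protocol bear on this.

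- **Measurement / Instrumentation** gives the CT dose and its timing together: "CT attenuation scan (0.8 mSv) will be acquired for attenuation correction and anatomic correlation prior to and after the emission scanning".
- **Subject Positioning on the PET/CT System** sets out the sequence. A CT-only surview comes first, and once the field is fixed "an attenuation CT scan of the imaging field will be acquired". No attenuation CT after emission appears there, and no dose is given for the surview.
- **Radiation Risk** counts the CT once at each dose level: "The attenuation CT will add 0.8 mSv EDE to the overall dose exposure". At level A, "the PET radiotracer will yield minimal radiation exposure of 0.64 mSv" and "the combined and total EDE is 1.44 mSv". At level B, "participants will receive a minimal radiation exposure of 1.90 mSv", "so the combined and total EDE is 2.70 mSv". The equivalents in natural background follow from these two totals, and the level A paragraph ends by calling the risk minimal.
- **Participant Procedures, Imaging Volunteers** allows a repeat of the tracer imaging at least a week later: "Subjects may enroll up to two times". Radiation Risk does not mention a second session and does not label its totals as per session.

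**The concern.** The exposure statement should describe the procedures that the protocol prescribes and permits. Here the sections do not agree on whether an attenuation CT follows emission, and it is unclear whether 0.8 mSv is the dose of one scan or of all attenuation CT in a session. Separately, a figure presented as the total takes no account of the second imaging session that the protocol allows.

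The subjects are healthy volunteers with no direct benefit, and these totals are the protocol's description of their radiation exposure. If the CT is acquired twice at 0.8 mSv, the per-session figure and its background equivalent are too low. If it is not, the figures hold for one session, but a subject who returns is not covered by them.

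**Working it through.** **Inputs.** Tracer dose T = 0.64 mSv (A) and 1.90 mSv (B), and background 3.6 mSv per year, all from Radiation Risk. CT dose per session C = 0.8 mSv as counted in Radiation Risk, or 2 × 0.8 = 1.6 mSv if Measurement / Instrumentation means two scans at 0.8 mSv each. Sessions N = 1 or 2, from Participant Procedures. The surview is left out because its dose is not given.

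**Formulas.** EDE = sum over sessions of (T + C). Days of background = EDE / 3.6 × 365.

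**The protocol's own figures.** A: 0.64 + 0.8 = 1.44 mSv, and 1.44 / 3.6 × 365 = 146 days. B: 1.90 + 0.8 = 2.70 mSv, and 2.70 / 3.6 × 365 = 274 days. Both reproduce exactly, with 0.8 mSv of CT and one session.

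**One session, two scans at 0.8 mSv each.**
- A: 0.64 + 1.6 = 2.24 mSv; 2.24 / 1.44 = 1.56; 2.24 / 3.6 × 365 = 227 days.
- B: 1.90 + 1.6 = 3.50 mSv; 3.50 / 2.70 = 1.30; 3.50 / 3.6 × 365 = 355 days.

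**Two sessions.**

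| Sessions | 0.8 mSv CT per session | 1.6 mSv CT per session |
|---|---|---|
| A + A | 2 × 1.44 = 2.88 mSv (292 days) | 2 × 2.24 = 4.48 mSv (454 days) |
| A + B | 1.44 + 2.70 = 4.14 mSv (420 days) | 2.24 + 3.50 = 5.74 mSv (582 days) |
| B + B | 2 × 2.70 = 5.40 mSv (548 days) | 2 × 3.50 = 7.00 mSv (710 days) |

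The A + B row assumes that a subject imaged at level A may return after the dosage has been raised. The protocol raises it for later participants and does not exclude this.

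**Sensitivity to the tracer-dose basis.** Radiation Risk says that only part of the loaded activity is inhaled, and the ¹¹C Dose section expects a release of 15 ± 5%. It is not stated whether 0.64 and 1.90 mSv already reflect this. The doses per loaded mCi, 0.64 / 3 = 0.213 and 1.90 / 9 = 0.211, are nearly equal and fit either basis. Suppose, as an assumption, that the figures are for the full cartridge and that a fraction f = 0.10 to 0.20 is released. Then EDE = N × (f × T + C):

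| CT per session | Sessions | A (mSv) | B (mSv) |
|---|---|---|---|
| 0.8 mSv | 1 | 0.86–0.93 | 0.99–1.18 |
| 0.8 mSv | 2 | 1.73–1.86 | 1.98–2.36 |
| 1.6 mSv | 1 | 1.66–1.73 | 1.79–1.98 |
| 1.6 mSv | 2 | 3.33–3.46 | 3.58–3.96 |

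On that basis level A exceeds 1.44 mSv with either a second CT or a second session. Level B exceeds 2.70 mSv only with both.

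**The case against.** The strongest reply is that Measurement / Instrumentation is the outlier. Its sentence has one subject and one dose, so 0.8 mSv could cover both acquisitions. Subject Positioning has a single attenuation CT before emission. Imaging Visit goes from the end of PET straight to de-gowning. The time budget under Imaging lists no second CT, although its items come to at most 15 + 5 + 2 + 60 = 82 of the 85 minutes. If only one CT is done, or 0.8 mSv covers both, the single-session totals are right.

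This stands, and it limits the point. A reader might infer that 1.44 and 2.70 mSv are arithmetic errors, or that a single session is certainly understated by 56% and 30%. The documents do not support that. The sums are correct, and the excess appears only if two scans are done at 0.8 mSv each. The sections could even be compatible if 0.8 mSv is a session figure and the positioning section simply omits the later scan.

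It can also be said that the repeat is optional and that each total is tied to one dosage. That is fair: as per-session figures they contradict nothing. They are nevertheless called totals, with no cumulative figure for a repeat that the protocol permits. The largest value, 7.00 mSv, needs two scans per session, both sessions at level B and the tracer doses as stated. It is an upper case, not an expected exposure.

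Finally, no aim, sample size or analysis depends on this, and a single session stays below the 3.6 mSv annual comparator on either CT reading. That bears on the size of the problem and does not remove the mismatch.

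**Conclusion.** The point holds as an inconsistency and an incomplete exposure statement.

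- **CT count and dose.** Measurement / Instrumentation, Subject Positioning and Radiation Risk need to be reconciled. The natural reading of the first is 0.8 mSv per scan and two scans. With the stated tracer doses, a session is then 2.24 mSv at A and 3.50 mSv at B. On the other reading 1.44 and 2.70 mSv stand, per session. The text does not settle which applies.
- **Second session.** This part does not depend on how the CT sentence is read. With the stated tracer doses, the printed totals are not the maximum permitted exposure: two sessions give 2.88 to 5.40 mSv with 0.8 mSv of CT each, or 4.48 to 7.00 mSv with 1.6 mSv each.
- **Tracer basis.** All of these sizes assume that 0.64 and 1.90 mSv are what a subject receives. If they are full-cartridge figures, the excess shrinks and at level B can disappear, and the printed totals would then misstate a session for another reason.

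A reader might also infer that subjects are given wrong figures. The consent text is not available, so that cannot be said.

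**What to change.** 1. Reconcile Measurement / Instrumentation, Subject Positioning and Radiation Risk on how many attenuation CTs a session includes, and state whether 0.8 mSv is per scan or per session. Say whether the surview dose is included.
2. State whether 0.64 and 1.90 mSv assume the full cartridge activity or the inhaled fraction.
3. Restate the EDE, background equivalents and risk estimates in Radiation Risk for the CTs actually acquired, and label them per session.
4. Add the cumulative EDE and its background equivalent for a subject who uses the second enrolment, including a mixed A and B pair if that is allowed.
5. Check that the consent text carries the same figures.

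The cost is wording and a short recalculation. Design, sample size and analysis are untouched. The stated exposure may look less favourable, at least for a subject who is imaged twice.
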